SAR442720 and pembrolizumab will be administered on a continuous basis, with SAR442720 administered orally at the RP2D determined from Part-1, and pembrolizumab administered intravenously at 200 mg Q3W or 400 mg Q6W. The SAR442720 tablet formulation (test) will be administered during the first cycle (21 days), and starting from C2D1, SAR442720 capsule formulation (reference) will be administered until the end of treatment (EOT). On C1D1, each participant will receive SAR442720 tablet in combination with pembrolizumab with a moderate-calorie moderate-fat breakfast after an overnight fast of 10 hours. The breakfast should be consumed within 0.5 hour, and there should be another 4 hour fast after the completion of breakfast. On C1D15, each participant will receive SAR442720 tablet after a 10 hour overnight fast prior to dosing on C1D15, followed by a 4 hour fast postdose. On C2D1, each participant will receive SAR442720 capsule in combination with pembrolizumab after a 10 hour overnight fast prior to dosing on C2D1, followed by a 4 hour fast postdose. For all other days (except for C1D1, C1D15, and C2D1), participants will be fasted for 1 hour prior and 1 hour after each SAR442720 dose. Water will be permitted ad lib for participants in either fasted or fed state, except for 1 hour before and 1 hour after the administration of SAR442720. Participants will be instructed to take SAR442720 with 240 mL of water.

Disclosure Statement: This is a non-randomized study with SAR442720 in combination with other agents (pembrolizumab or adagrasib) with no masking in participants with advanced malignancies.

Number of participants:

Approximately 18 to 24 DLT evaluable participants are expected to be enrolled during the Dose Escalation and mini-expansion cohort (Part-1). It assumes 3 combination dose levels (as shown above) with 3 to 6 participants per dose level. At least 6 participants need to be treated at the MTD. After the MTD is identified, another 6 participants will be treated at the MTD to confirm the decision and determine the RP2D. The actual sample size will vary depending on DLTs observed and the number of dose levels explored.

In Part-2 approximately 40 participants will be enrolled and treated at RP2D determined from Part-1. It is planned to enroll 20 participants with PD-L1 TPS $\geq 50\%$ (Cohort A1) and 20 participants with PD-L1 TPS in 1-49% (Cohort A2).

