In Part-3A, approximately 15-30 DLT evaluable participants are expected to be enrolled. In Part-3B, approximately 40 participants at the RP2D determined from Part-3A will be enrolled.

In Part-4, up to approximately 12 participants will be enrolled.

“Note: Enrolled participants are all participants from screened participants who have been allocated to an intervention regardless of whether the intervention was received or not”.

Intervention groups and study duration:

Part-1 and Part-4

The duration of the study for a participant will include a period for screening of up to 28 days. Participants will be evaluated for safety and tolerability. Once successfully screened, enrolled participants may receive study intervention until disease progression, unacceptable AE, or the participant's or investigator's decision to stop the treatment. Each cycle of treatment will have duration of 21 days. After discontinuing study intervention, participants will return to the study site approximately 30 days after the last IMP administration or before the participant receives another anti-cancer therapy, whichever is earlier, for end-of-treatment assessments. Participants without documented disease progression at the end of a treatment visit who have not yet started treatment with another anti-cancer therapy will proceed with 3 months follow-up visits until initiation of another anti-cancer therapy, disease progression, death, or study cutoff date (whichever comes first). The expected duration of study intervention for participants may vary, based on progression date; median expected duration of study per participant is estimated to be 10 months (up to 1 month for screening, a median of 6 months for treatment, and a median of 3 months for long term follow-up).

Part-2 and Part-3

The duration of the study for a participant will include:

- Screening period: up to 28 days.
- Treatment Period: enrolled participants will receive continuous treatment until PD, unacceptable AE, and other full permanent discontinuation criteria as described in [Section 7.1](#).
- End of treatment and Follow-up: EOT visit will occur 30 days \pm 5 days from last IMP administration or prior to initiation of further therapy. Participants will then enter the follow up (not applicable to Part-3) and will be followed differently depending on the reason leading to EOT:

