- Dose regimen: Pembrolizumab will be administered at 200 mg via IV infusion over 30 minutes Q3W or 400 mg via IV infusion over 30 minutes Q6W (for Part-2 and Part-4) in accordance with the label as mentioned in [Section 6.1.1](#).

Adagrasib (Part-3 only)

- Formulation: MRTX849 is supplied as immediate release film-coated tablets of 200 mg. The tablets are packaged in HDPE bottles.
- Route of administration: Oral with at least 240 mL (8 ounces) of water; may be taken with or without food. When co-administered with SAR442720, adagrasib should be taken without food (as SAR442720).
- Dose regimen: Adagrasib will be administered orally BID (two times a day) each day. The starting dose is 400 mg BID each day; this should be at 12-hour intervals to the extent possible.

Statistical considerations:

Part-1

- **Primary endpoint:** The primary endpoints in the Part-1 are incidence, nature, and severity of DLTs, AEs, and SAEs. The treatment-emergent adverse event (TEAE) period is defined as the time from the first dose of study interventions up to 30 days after last dose of study interventions. The number and percentage of participants experiencing TEAEs by primary system organ class and preferred term (PT) will be summarized by NCI CTCAE Version 5.0 grade (all grades and Grade ≥ 3). Similar tables will be prepared for treatment-related TEAEs, adverse event of special interest (AESIs), TEAEs leading to treatment discontinuation, TEAEs leading to dose modification, delay or omission, serious TEAEs and TEAEs with fatal outcome.
- **Main secondary endpoints:** Secondary endpoints include laboratory results, ORR, duration of response (DoR), and PK concentrations.

Clinical laboratory test results will be graded according to NCI CTCAE Version 5.0, when applicable. Number (%) of participants with laboratory abnormalities (ie, all grades and Grade ≥ 3) using the worst grade during the TEAE period will be provided for all-treated population.

The ORR per RECIST v1.1 will be summarized with descriptive statistics with a 90% 2-sided confidence interval (CI). DoR will be analyzed using Kaplan-Meier method.

PK concentrations of SAR442720 and pembrolizumab will be summarized with descriptive statistics.

Part-2

- **Primary endpoint:** The primary endpoint in the Part-2 is ORR. The ORR per RECIST v1.1 will be summarized with descriptive statistics with a 90% 2-sided CI.

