Fresh tumor biopsy			X			X		X		Fresh tumor biopsies (applicable to Part-1 only) pre-treatment and C2D15 will be mandatory for participants enrolled in the study, unless the investigator determines that the tumor site is not amenable to biopsy and poses a significant risk to participant safety. The Sponsor will evaluate this requirement on a case-by-case basis, and archival tumor tissue should not be used to replace fresh tumor biopsy in more than 6 participants. Pre-treatment biopsy may be a biopsy which was completed within 6 months prior to C1D1 without any anti-cancer treatment administered in such timeframe. The on-treatment biopsy may be obtained at C2D15 with a window of ±7 days. Pre-treatment and on-treatment biopsy (C2D15 with a window of ±7 days) should be collected from the same lesion. An EOT biopsy will be requested but is not mandatory. See Section 8.6 .

Procedure (Part-1 and Part-4)	Screening ^a		Cycle 1 (21-day cycle)			Cycles 2+ (21-day cycle)		EOT (within 30 ±5d of last dose) ^b	LTFU (every 3 months ±2 wks) ^c	Notes E/D=Early Discontinuation
Day	-1 to -28	-1 to -14	1	8 (±1 d)	15 (±1 d)	1 (±2 d)	15 (±2 d)			
Blood for immune cell profiling, cytokines, RNA and ctDNA biomarker			See Table 9 below (Part-1 only)							
Study intervention										
SAR442720 dosing			Continuous dosing (twice weekly)							SAR442720 is administrated orally at home or at the hospital. See Section 6.1 .
Pembrolizumab dosing			Continuous dosing Q3W (Part-1 and Part-4) or Q6W (Part-4 only)							Pembrolizumab is administrated in IV infusion at the hospital. See Section 6.1 .
Assessment and documentation of study compliance			←=====→							Participants should be instructed to bring their pills and diary to every visit.
AE review		X	←=====→			X				C1D1 predose and See Section 8.3 .
SAE review		X	←=====→			X				C1D1 predose and See Section 8.3 .
Concomitant medication review		X	←=====→			X				Record all concomitant medications including any prescription medications, over-the-counter preparations, and transfusions received by participant from 7 days preceding C1D1 through EOT.
PK assessments										
Plasma samples			See Table 5 (Part-1) and Table 8 (Part-4) below							Blood samples (1.5 mL/sample) will be collected and processed into plasma for SAR442720 PK analysis at the time points listed in Table 5 (Part-1) and Table 8 (Part-4).

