SAR442720 and pembrolizumab will be administered on a continuous basis, with SAR442720 administered orally at the RP2D determined from Part-1, and pembrolizumab administered intravenously at 200 mg Q3W or 400 mg Q6W. The SAR442720 tablet formulation (test) will be administered during the first cycle (21 days), and starting from C2D1, SAR442720 capsule formulation (reference) will be administered until the EOT. On C1D1, each participant will receive SAR442720 tablet in combination with pembrolizumab with a moderate-calorie moderate-fat breakfast after an overnight fast of 10 hours. The breakfast should be consumed within 0.5 hour, and there should be another 4 hour fast after the completion of breakfast. On C1D15, each participant will receive SAR44272 tablet in combination with pembrolizumab after a 10 hour overnight fast prior to dosing on C1D15, followed by a 4 hour fast postdose. On C2D1, each participant will receive SAR442720 capsule in combination with pembrolizumab after a 10 hour overnight fast prior to dosing on C2D1, followed by a 4 hour fast postdose. For all other days (except for C1D1, C1D15, and C2D1), participants will be fasted for 1 hour prior and 1 hour after each SAR442720 dose. Water will be permitted for participants in either fasted or fed state, except for 1 hour before and 1 hour after the administration of SAR442720. Participants will be instructed to take SAR442720 with 240 mL of water. The menu options for the fed cohort are shown in Appendix 13 ([Section 10.13](#)). The timing of sample collection for PK of SA4442720 and pembrolizumab is presented in [Table 8](#). In Part-4, up to approximately 12 participants are expected to be enrolled.

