4.3 JUSTIFICATION FOR DOSE

Part-1 (SAR442720)

The starting dose of SAR442720 is selected based on ongoing clinical trials. The starting dose of SAR442720 is 140 mg Day 1 and Day 4 BIW, [REDACTED]

[REDACTED] Please refer to RMC 4630 IB for more details. Given the overall safety profile based on the available clinical data on pembrolizumab and SAR442720 monotherapy, the starting dose of SAR442720 in this combination study is 140 mg administered orally BIW (Day 1 and Day 4 schedule) in a 21-day cycle. During the study, alternative BIW dose schedules, such as Day 1 and Day 2 of each week, or any other emergent dose schedule from the ongoing Phase 1 monotherapy escalation study can be explored after agreement of the Study Committee.

Part-2 (SAR442720)

Part-2 of the study will start once RP2D for SAR442720 from Part-1 is confirmed. The dose of SAR442720 in Part-2 will be the RP2D, which will be the highest cleared dose from Part-1 which will most likely be 200 mg BIW, such as D1 and D2 of each week.

The dose of pembrolizumab for Part-1 and Part-2 is the fixed recommended dose of 200 mg IV Q3W or 400 mg IV Q6W.

Part-3 (SAR442720 and adagrasib)

The starting dose of SAR442720 is selected based on the preliminary clinical safety and tolerability observed in Phase 1 RMC-4630-01 monotherapy study. A dose of 200 mg BIW Day 1 Day 2 SAR442720 has been cleared by the Dose Committee and selected as the RP2D for the final expansion cohort. SAR442720 is identified as a CYP3A and P-gp substrate, with CYP3A contributing to approximately [REDACTED] of total hepatocyte metabolism. Adagrasib is a strong inhibitor of CYP3A and a weak inhibitor of P-gp, which may increase SAR442720 exposure up to [REDACTED] (mainly due to CYP3A inhibition). Therefore, the starting dose of SAR442720 is selected to be [REDACTED] less than the RP2D at monotherapy, which is 100 mg Day 1, Day 2 (D1D2).

SAR442720 is not anticipated to alter the PK of adagrasib.

Part-4 (SAR442720)

Part-4 of the study will start at the RP2D for SAR442720 from Part-1, the highest cleared dose from Part-1, which is 200 mg BIW, administered on D1 and D2 of each week. This dose has been cleared by the Dose Committee and selected as the RP2D for the combination of SAR442720 and pembrolizumab.

The dose of pembrolizumab for Part-4 is the fixed recommended dose of 200 mg IV Q3W or 400 mg IV Q6W.

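### Part-4: Section 4.1 places pembrolizumab on C1D15, a day on neither permitted schedule, and the C2D1 instruction makes no exception for Q6W participants

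*Protocol*

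**What the plan says.** In Section 4.1, the Part-4 paragraph on dosing opens with the regimen: "pembrolizumab administered intravenously at 200 mg Q3W or 400 mg Q6W". It then gives instructions for the three PK days.

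- **C1D1:** tablet with pembrolizumab, fed.
- **C1D15:** "On C1D15, each participant will receive SAR44272 tablet in combination with pembrolizumab after a 10 hour overnight fast prior to dosing on C1D15".
- **C2D1:** "On C2D1, each participant will receive SAR442720 capsule in combination with pembrolizumab after a 10 hour overnight fast prior to dosing on C2D1".

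The synopsis has a near-identical paragraph. Its C1D1 and C2D1 sentences match on pembrolizumab, but its C1D15 sentence does not: "On C1D15, each participant will receive SAR442720 tablet after a 10 hour overnight fast prior to dosing on C1D15".

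The permitted regimen is stated consistently in several other places:

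- The synopsis dose-regimen entry allows 200 mg Q3W or "400 mg via IV infusion over 30 minutes Q6W (for Part-2 and Part-4) in accordance with the label".
- Section 4.3 says: "The dose of pembrolizumab for Part-4 is the fixed recommended dose of 200 mg IV Q3W or 400 mg IV Q6W".
- The pembrolizumab row of Table 2 (Section 1.3) allows Q3W, or Q6W in Part-4 only.
- For Part-1 and Part-4 the synopsis sets the cycle length: "Each cycle of treatment will have duration of 21 days".

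Table 16 mentions Q6W for Part-2 only, but the places above all extend it to Part-4.

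**The concern.** The C1D15 sentence is an operative dosing instruction, and it puts an infusion on a day that the regimen in its own paragraph does not allow. A site cannot follow both that sentence and the Q3W or Q6W interval in Table 2, yet Section 8 makes adherence to the design and the schedule of activities essential. The C2D1 sentence raises the same problem for anyone on Q6W.

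What is at stake is an unscheduled infusion of an investigational product, or an avoidable query or deviation. One smaller effect concerns the SAP. Its PK-evaluable population for Part-4 (Section 3, Table 3) requires no missed doses on C1D1, C1D15 and C2D1 without naming the drug. Protocol Section 6.6 suggests that SAR442720 is meant, but a sentence placing pembrolizumab on C1D15 leaves room for doubt.

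The PK comparisons themselves are not in question. Section 2.3.1.3 does not expect pembrolizumab to affect SAR442720 PK, and Section 8.9 describes its exposure-response for safety as flat. No claim is made that the protocol's overdose definition would be met.

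**Working it through.** **Inputs.** Cycle length 21 days (synopsis, Part-1 and Part-4). Pembrolizumab 200 mg every 21 days or 400 mg every 42 days (Sections 4.1 and 4.3, Table 2). Visit windows from Table 2: C1D15 ±1 day; Day 1 of Cycle 2 and later ±2 days. Part-4 size: up to approximately 12 (Section 4.1). The number on Q6W is not given, so it is taken as k = 0 to 12.

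**Infusion days.** Q3W days are 1 + 21j and Q6W days are 1 + 42j, for j = 0, 1, 2, …

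| Visit | Study day | Q3W infusion due? | Q6W infusion due? | Pembrolizumab in Section 4.1 | Pembrolizumab in synopsis |
|---|---|---|---|---|---|
| C1D1 | 1 | yes | yes | yes | yes |
| C1D15 | 15 | no | no | **yes** | no |
| C2D1 | 1 + 21 = 22 | yes | **no** | yes, everyone | yes, everyone |
| C3D1 | 1 + 42 = 43 | yes | yes | not addressed | not addressed |

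**Do the visit windows explain it?** C1D15 spans Days 14 to 16 and C2D1 spans Days 20 to 24. The nearest days are 20 − 16 = 4 days apart, so they do not.

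**Supporting text.** Table 8 schedules pembrolizumab samples on C1D1, C2D1 and C6D1 and has none on Day 15. The SAP (Sections 4.7.1.1 and 4.7.1.3) derives pembrolizumab exposure only from intervals of 20 or 41 days after the last dose. Both fit a regimen without a Day 15 infusion.

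**Size if read literally.** The sentences give no dose, so each extra infusion is assumed to be at the participant's own regimen dose.

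- Q3W participant: literal days 1, 15, 22 against scheduled days 1, 22. Extra: Day 15, so 1 × 200 mg.
- Q6W participant: literal days 1, 15, 22 against scheduled days 1, 43. Extra: Days 15 and 22, so 2 × 400 mg.
- All of Part-4 with 12 participants: the C1D15 sentence adds 12 and the C2D1 sentence adds k, giving 12 + k. That is 12 when k = 0 and 24 when k = 12.
- After correcting C1D15 only: k remain (0 to 12). After correcting both: 0.

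**The case against.** The strongest counter-argument is that the phrase about combination with pembrolizumab describes the background regimen and does not order an infusion that day. The Part-4 endpoints in Section 3 use it in that sense for tablets under fed and fasted conditions, and the fasted tablet profile is the one taken on C1D15. On that reading the C1D15 sentence is loose wording and the C2D1 sentence is correct for both schedules. Misdosing is also unlikely: the regimen opens the same paragraph, infusions are given in hospital (Table 2), a second staff member confirms doses given on site (Section 6.4), and a Pharmacy Manual holds further product detail (Section 6.1.1).

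Some of this stands. The benign reading is possible, and the infusion counts are an upper limit that requires every site to take the text literally. The conflict with Table 2 is inferred from the dosing interval, because that row spans the cycle without day-by-day marks; the only direct textual conflict on C1D15 is with the synopsis. On C2D1 the synopsis and Section 4.1 agree, so the fault there is only against the permitted Q6W option.

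It does not remove the defect. These are three parallel dosing sentences. In the first the phrase marks a real infusion day for everyone, and in the third it does so for Q3W participants, so nothing tells a reader to take the middle one differently. The synopsis drops the phrase on exactly the one of the three days when no infusion is due under either schedule.

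**Conclusion.** The concern holds. Section 4.1 is wrong as written on C1D15: it conflicts with the synopsis and with both permitted pembrolizumab intervals. The C2D1 sentence, in Section 4.1 and the synopsis alike, is wrong for any Part-4 participant on 400 mg Q6W.

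Read literally, the result is one unscheduled infusion per Q3W participant and two per Q6W participant, or 12 to 24 in total. That range assumes 12 participants, k between 0 and 12 on Q6W, and the literal reading applied throughout. The realistic number is probably much lower, and no endpoint, sample size or analysis figure depends on it. It should be corrected because it governs when an intravenous investigational drug is given; it is not a critical flaw in the design.

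**What to change.** 1. In Section 4.1, remove the reference to pembrolizumab from the C1D15 sentence so that it agrees with the synopsis. The drug code in that sentence also lacks its final digit and can be corrected at the same time.
2. In both Section 4.1 and the synopsis, reword the C2D1 sentence along these lines: *On C2D1 all participants take the SAR442720 capsule fasted; those on pembrolizumab 200 mg Q3W also receive their infusion, while those on 400 mg Q6W are next infused on C3D1.*

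A related tidy-up, if wanted: the Day 15 predose row of Table 8 carries the footnote about simultaneous SAR442720 and pembrolizumab samples, although no pembrolizumab sample is listed there.

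The cost is wording in three sentences, with no change to sample size, assessments or analysis. Section 10.1.1 requires IRB/IEC approval before design changes made by amendment are implemented, so a clarification to sites, or inclusion in the next amendment, would be proportionate.

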4.1.1 Dose-limiting toxicity criteria (Part-1 and Part-3A)

Potential DLTs are defined as all AEs specified below occurring during the first cycle of treatment considered by the investigator to be related to study treatment, unless due to disease progression or to a cause obviously unrelated to IMP.

- Grade ≥ 4 AEs.
- Grade 3 neutropenia lasting > 7 days or febrile neutropenia.
- Grade 3 thrombocytopenia with clinically significant bleeding.
- Any Grade ≥ 3 immune-related AEs (irAE) (Part-1, 2, and 4 only).

An irAE can occur shortly after the first dose or several months after the last dose of treatment. All AEs of unknown etiology associated with drug exposure should be evaluated to determine possible immune etiology. If an irAE is suspected, efforts should be made to rule out neoplastic, infectious, metabolic, toxin or other etiologic causes prior to labeling an AE as an irAE.

- Grade 3 nonhematologic AEs, including rash, nausea/vomiting, hypertension, diarrhea, retinopathy, or blurred vision that remain uncontrolled (does not resolve to \leq Grade 2) for > 72 hours despite maximal supportive care. Electrolyte abnormalities or Grade 3 asymptomatic creatine phosphokinase (CPK) or gamma-glutamyl transferase (GGT) elevations that are corrected within 72 hours will not be considered DLTs.
- Grade 3AST, ALT, and/or total bilirubin elevations that persist > 5 days.

- Concurrent elevation of AST or ALT $>3 \times$ upper limit of normal (ULN) and total bilirubin $>2 \times$ ULN or international normalized ratio (INR) >1.5 in the absence of cholestasis and other causes (eg, viral hepatitis, other pre-existing or acute liver disease, or another drug capable of the observed injury), which may indicate severe drug-induced liver injury (possible Hy's law case).
- Grade 3 QTcF (defined as QT interval corrected using Fridericia's formula [QTcF] >450 msec or change from baseline of QTcF >50 msec) prolongation.
- Retinal vein occlusion (RVO) any grade
- Toxicity related to IMP leading to 50% or less dose intensity of SAR442720 (eg, miss ≥ 3 doses) and/or delay in initiation of Cycle 2 dosing of pembrolizumab by >15 days, in the absence of recovery to baseline or Grade ≤ 1 (except for alopecia, vitiligo, fatigue and thyroiditis) AE. Toxicity resulting in the inability to deliver at least 66.7% of the dose of adagrasib (Part-3A) as intended for the duration of the cycle.
- An absolute decrease in LVEF of 20 percentage points or greater from the baseline value to a value that is below the institutional lower limit of normal (LLN) value, OR symptomatic systolic dysfunction with LVEF decrease from baseline $\geq 10\%$ and/or below LLN.

At the end of Cycle 1, each participant must be assessed by the Investigator to determine if he or she experienced a DLT. This information must be recorded on the appropriate electronic case report forms (eCRFs), and an electronic DLT notification (either DLT or not) will be sent to the Sponsor, before a subsequent cycle may begin.

Potential and IMP related DLTs will be considered as AESIs. As such, Investigators are required to report them to the Sponsor within 24 hours of the Investigator becoming aware of each AE. The Investigator will attach the DLT-specific case report form (CRF) page to the transmitted DLT/AESI form or will complete the specific DLT form in the eCRF.

The reported potential DLTs will be reviewed by the Sponsor and recruiting Investigators in order to determine their relationship to the IMP and confirm them as DLTs.

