4.1.2 Dose escalation

In Part-1 and Part-3A, dose escalation will follow mTPI2 design with a minimum of 3 participants evaluable for DLT in the first cycle. A participant will be considered evaluable for DLT assessment if he/she receives at least 4 out of the 6 planned doses of SAR442720 in the first cycle and completes the DLT observation period or if he/she experiences a DLT in the DLT observation period. A participant who is not DLT-evaluable will be replaced to achieve a minimum of 3 DLT-evaluable participants at the same cohort.

The actual dose selected at each dose escalation decision, and the MTD identified at the conclusion of the dose escalation phase, will be determined by the Study Committee, in agreement with the Sponsor's Study Medical Manager, which may select a dose at or below the model's recommendation and should not select a dose that is suggested to be over toxic by the model. The Study Committee will review the overall safety of all dose levels. More details in the model and its operating characteristics can be found in Appendix 11 ([Section 10.11](#)).

The adaptive dose escalation design is based on the boundaries generated from the mTPI2 design. The dose escalation will stop if the next recommended dose has been collectively evaluated in at least 2 previous escalation cohorts.

It is anticipated that in Part-1 12 to 18 DLT-evaluable participants and in Part-3A 15 to 30 DLT-evaluable participants will be enrolled in the dose escalation. The actual total number of participants required will depend on the number of dose levels evaluated and on the incidence and timing of observed DLTs.

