**Table 3 - Populations for analyses**

Population	Description
Enrolled	All participants who sign the ICF and have dose allocated to an intervention regardless of whether the intervention was received or not.
DLT-evaluable (only for Part-1 and Part-3A)	
Patients who take at least 4 of the 6 planned doses of SAR442720 (Part-1 and Part-3A) and 28 of the 42 planned doses of adagrasib (Part-3A) in the first cycle of the treatment and complete the DLT observation period.
 
OR
 
Patients who have any DLT observed in the DLT observation period.

PK	Patients who have at least one measurable SAR442720 concentration or at least one measurable pembrolizumab concentration after the first dose or at least one measurable adagrasib concentration after the first dose.
PD	Patients who have at least one PD marker result after the first dose
Safety	Patients who take at least one dose of any IMP (i.e., SAR442720, pembrolizumab, or adagrasib)
PK evaluable (Part-4 only)	Patients who complete all of cycle 1 and C2D1 with meal information, full PK, and no dose reduction/missed doses on C1D1, C1D15 and C2D1. Missing some PK samples may still be considered as evaluable and will be assessed case-by-cased.

Abbreviations: DLT = dose-limiting toxicity, ICF = informed consent form, PD = pharmacodynamic(s), PK = pharmacokinetic(s)

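### On one natural reading, a participant who loses half or more of the SAR442720 doses to toxicity that recovers is neither a DLT nor DLT-evaluable; the 80% rule in Part-3A opens a second gap

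*Protocol*

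**What the plan says.** **DLT criterion (Protocol 4.1.1).** One bullet has two limbs for the pembrolizumab combination, followed by a condition. The first limb is "Toxicity related to IMP leading to 50% or less dose intensity of SAR442720 (eg, miss" three or more doses). The second limb and the condition read "and/or delay in initiation of Cycle 2 dosing of pembrolizumab by >15 days, in the absence of recovery to baseline or Grade" 1 or lower, with a few AE types exempted. The text does not say whether the condition governs one limb or both, or as of when recovery is judged. A separate sentence covers adagrasib, with no recovery condition: "Toxicity resulting in the inability to deliver at least 66.7% of the dose of adagrasib (Part-3A) as intended for the duration of the cycle".

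**Evaluability (Protocol 4.1.2).** A participant counts if he or she "receives at least 4 out of the 6 planned doses of SAR442720 in the first cycle and completes the DLT observation period". The only other route to evaluability is a DLT within that same window. Protocol Table 20 and SAP Table 3 ("Patients who take at least 4 of the 6 planned doses of SAR442720 (Part-1 and Part-3A") use the same 4 of 6 and add 28 of 42 adagrasib doses for Part-3A. The Synopsis and Section 4.1 give a different Part-3A rule: at least 80% of the scheduled Cycle 1 dose of both drugs.

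**Replacement (Protocol 4.1.2).** "A participant who is not DLT-evaluable will be replaced to achieve a minimum of 3 DLT-evaluable participants at the same cohort".

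**Use.** Protocol 9.4.1 and SAP 4.1 base the MTD recommendation on Cycle 1 data from the DLT-evaluable population only.

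**The concern.** Whether a participant is evaluable should not depend on toxicity, unless that toxicity is itself scored. Here the missed-dose limb and the 4-of-6 rule are exact complements. A participant who loses three or more doses is therefore evaluable only if the course is a DLT. If recovery removes DLT status, the course has no place in the model's counts, although the drug could not be given as planned.

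The MTD is a primary objective of Part-3A, levels hold only 3 to 6 participants, and about 40 Part-3B participants are treated at the resulting RP2D. With counts this small, one course can change a dose decision. The unclear scope is a problem in its own right, because two investigators could classify the same course in opposite ways.

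**Working it through.** **1. Thresholds.** Missing 3 of 6 is 3/6 = 50% dose intensity, as 4.1.1 states. Evaluability needs 4/6 = 66.7%. No dose count lies between them, so every participant in the missed-dose limb fails 4 of 6. For adagrasib, 28/42 = 66.7% matches the adagrasib DLT threshold, so that pair leaves no gap.

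**2. Readings of the recovery condition.**

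| Reading | Recovered course, 3 or more doses lost, no other DLT bullet met |
|---|---|
| Covers both limbs, recovery at any later time | Not a DLT, not evaluable, may be replaced |
| Covers only the Cycle 2 delay | DLT, counted |
| Means unrecovered while doses were being missed | DLT, counted |

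**3. A route.** Grade 3 thrombocytopenia without bleeding is not a DLT in 4.1.1, yet Table 27 holds both drugs until Grade 1 or better. On Day 1/Day 2 dosing, SAR442720 falls on days 1, 2, 8, 9, 15 and 16. An unbroken hold to the end of the cycle costs three doses only if it starts by Day 9.

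**4. Part-3A, both drugs held.** With SAR442720 taken alongside an adagrasib dose, I enumerated all unbroken joint holds. The shortest that costs three SAR442720 doses costs 15 adagrasib doses, leaving 27/42 = 64.3%, below 66.7%. The adagrasib limb then makes it a DLT. What remains is mainly SAR442720-only holds, which Table 27 describes for Grade 3 hypertension, some ocular events, and other AEs attributed to one drug.

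**5. Part-3A, 80% rule.** 0.8 × 6 = 4.8, so 5 doses; 0.8 × 42 = 33.6, so 34 doses. A participant who takes 4 of 6 SAR442720 doses because of toxicity has 66.7% intensity, so the 50% limb is not met, but is non-evaluable. The same holds for 28 to 33 adagrasib doses. No recovery condition is needed.

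**6. One level, one course.** Take 1 DLT plus 1 such course. As excluded and replaced (replacement without a DLT), the model sees 1/6; if counted, 2/6. mTPI2 with a Beta(1,1) prior and assumed targets:

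| Assumed target (interval) | 1/6 | 2/6 |
|---|---|---|
| 25% (20–30%) | escalate | de-escalate |
| 30% (25–33%) | escalate | de-escalate |
| 30% (25–35%) | escalate | stay |

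**7. Rate seen.** Let p be the true rate of dose-limiting courses, f the share lost through the gap, and q = pf. The model sees p if they are counted, (p − q)/(1 − q) if excluded, and p − q if kept as evaluable non-DLTs. At p = 0.33:

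| f | Rate seen if excluded | P(2 or more DLTs in 6) |
|---|---|---|
| 0 | 0.33 | 64% |
| 10% | 0.297/0.967 = 0.31 | 60% |
| 25% | 0.2475/0.9175 = 0.27 | 51% |
| 50% | 0.165/0.835 = 0.20 | 34% |

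**8. Simulated mTPI2** (cohorts of 3; stop when the next recommended dose already has 6; drop a dose if P(rate > target) > 0.95; 20,000 runs). True rates, f and targets are all assumed. Entries are the chance of selecting an over-toxic dose.

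| True rates; over-toxic dose | Assumed interval | Counted | f = 10% | f = 25% | f = 50% |
|---|---|---|---|---|---|
| 0.10/0.20/0.45; the 0.45 dose | 20–30% or 25–33% | 13% | 16% | 22–23% | 41% |
| same | 25–35% | 37% | 42% | 52% | 73% |
| 0.08/0.12/0.20/0.30/0.45/0.55; above 0.33 | 20–30% or 25–33% | 5% | 7% | 11% | 27% |
| same | 25–35% | 15% | 20% | 28% | 52% |

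The 25–35% rows are an outer case: the amendment history records a design change so that the upper limit does not exceed 33%. Keeping the same courses as evaluable non-DLTs raises the three-level figures to 18%, 29% and 54% (or 45%, 60% and 81%).

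**The case against.** A reader might infer that the MTD is biased upward and that replacement causes it. The documents do not support either statement.

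- **Scope.** Two of three readings of the recovery condition close the gap. This stands; the defect is that the text does not choose.
- **Other bullets.** Grade 4 events, uncontrolled Grade 3 non-hematologic events beyond 72 hours, and liver test elevations beyond 5 days are DLTs anyway. This stands and narrows the route.
- **Part-3A.** Joint holds of the needed length are DLTs through adagrasib. This stands, but not for SAR442720-only holds or the 80% rule.
- **Part-1.** The protocol already reports 200 mg on Day 1 and Day 2 as its outcome, so the forward-looking stake is Part-3A.
- **Frequency.** None is given. Monotherapy median onset and duration (Table 11) are 15 and 24 days for thrombocytopenia, 21.5 and 21.5 for anemia, 17 and 14.5 for edema, and 9 and 4 for diarrhea. The first three typically start after Day 9, and diarrhea typically resolves before three doses are lost. Small f is therefore more plausible, though medians do not exclude early cases.
- **Section 6.6** bars Cycle 1 modifications without a DLT, which read literally would prevent the hold. Tables 26 and 27 direct holds for events that are not DLTs, so these passages conflict and do not settle the point.
- **Safeguards.** All AEs not obviously unrelated inform the MTD and RP2D, and the committee may only select at or below the model. This stands and is why the final MTD may be unaffected. It is discretionary and does not correct the model's counts.
- **Replacement.** Because (p − q)/(1 − q) exceeds p − q, excluding these participants gives a higher rate than keeping them as non-DLTs. The shift comes from their not being scored as DLTs.

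**Conclusion.** The concern holds in limited form. On a natural reading of 4.1.1, a recovered toxicity that costs three or more SAR442720 doses and meets no other DLT bullet is neither a DLT nor evaluable, and drops out of the MTD data. The Part-3A 80% rule conflicts with 4/6 and 28/42 and creates a second, wider gap that starts at two missed SAR442720 doses.

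The direction for the model is fixed: the rate it sees is lower than if these courses were counted as DLTs. The size for the final MTD is unknown. In the assumed scenarios, selection of an over-toxic dose rises by 2 to 6 percentage points if 10% of dose-limiting courses are lost this way, and by 6 to 15 points at 25%. These figures depend on assumed frequencies and targets. Severity: should fix.

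**What to change.** 1. Reconcile the Synopsis and 4.1 (80% rule), 4.1.1, 4.1.2, protocol Table 20 and SAP Table 3 into one DLT-evaluable definition. State whether the recovery condition applies to the missed-dose limb, the Cycle 2 delay or both, and as of when. Which courses are DLTs is the sponsor's clinical decision. Section 6.6 and Tables 26 and 27 also need reconciling on Cycle 1 holds.
2. State that a participant below the minimum doses because of IMP-related toxicity is not replaced as non-evaluable, but is adjudicated and recorded as DLT or non-DLT before the next dose decision. Limit replacement to reasons unrelated to toxicity. This needs item 1: evaluability without a settled DLT rule would lower the rate the model sees still further.
3. Show each mTPI2 decision a second time with these participants counted as DLTs.

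The cost is a few sentences across the listed sections and one entry in the committee minutes per decision. Escalation may be slightly more cautious.
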